Adjusting Insulin Delivery to Activity (AIDA):

Use of Activity Data to Adjust Insulin Pump Therapy for Children with Type 1 Diabetes

AIDA Investigation Protocol

Investigators:

[name]
[name]
[name]
[name]

NCT: 022994479

Version Date: September 21, 2016

Summary/Abstract

Being diagnosed with type 1 diabetes at a young age places a lifelong burden on the child together with new challenges and responsibilities for the parents of that child. New technologies such as continuous glucose monitors (CGM) and high resolution insulin pumps with the ability to deliver the low basal rates required for very young children have reduced the burden, but the pumps need to be carefully configured with some of the setting needing to be subtly adjusted following exercise, which if performed later in the day has been shown to reduce the nighttime basal requirements. Many adults with type 1 diabetes (T1D) are able to intuitively make adjustments based on prior activity; however, parents of younger children may not even be aware of their child's activity levels while at day-care or school. Moreover, the amount and timing of the adjustments are not well defined and may be highly variable between subjects. The present study looks to assess the feasibility of combining new generation activity monitors (FitBit or similar), with data obtained from CGM and insulin pump records to improve insulin dose adjustments and prevent hypoglycemia in the pediatric population.

Abbreviations: SAP – sensor augmented pump therapy; CGM – continuous glucose monitor; T1D – type 1 diabetes; TDD – total daily dose;

1. Specific Aim:

To determine the feasibility of using activity monitor data to predict the need to make temporary insulin pump dose adjustments to prevent nighttime hypoglycemia.

2. Background and significance

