The initial 2 weeks of a subject's enrollment in the study will be used to establish his or her baseline activity level and no changes to the insulin regimen will be made based on the activity monitor data. During weeks 3-6 to 12-16, activity data will be reviewed daily and an alternate basal insulin rate will be recommended on days considered to be increased activity days. We will use an adaptive algorithm to help guide suggested nighttime insulin basal rate changes. All recommendations will be reviewed and approved by a study physician prior to implementation. The alternate rate will be derived using the subject's usual care pump settings as an initial starting point from which to make incremental changes in the 3 hour interval leading up to the hypoglycemic event. Target will be the overnight nadir obtained with usual care settings. Residual error (CGM-target) will be used to assess the validity of using the 3 hour window prior to the event to effect lower basal. The patient's primary diabetes team will be informed about the recommended nighttime basal insulin dose change and this will be documented in the patient's medical record in powerchart. The primary diabetes team will not give recommendations regarding nighttime insulin rate dose changes based on activity monitor data; however, they will continue to guide all other aspects of the patient's diabetes management.

b. Patient Selection and Inclusion/Exclusion Criteria

Subjects will be recruited from the outpatient endocrinology clinic based on physician recommendation and approval to approach at Boston Children's Hospital (BCH) as well as through public notice. 20 subjects will be recruited in two different age designations.

Inclusion Criteria:

- Age: 1 to 17 years old
- Type 1 diabetes (as clinically diagnosed by outpatient endocrinologist).
- Treated with insulin pump therapy for greater than or equal 3 months

- Families will need to have access to Wi-Fi and a compatible smartphone in order for the data from the activity monitor and other devices to be transmitted to the research team

Exclusion Criteria:

- Current glucocorticoid use or other medication known to affect insulin action at investigator's discretion.
- Hospitalization within the last month

c. **Description of Study Treatments and Procedures**

RECRUITMENT, SCREENING AND CONSENT:

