instructed to calibrate the CGM a minimum of twice daily, before breakfast and before going to bed. Additional calibrations may be performed at the subject's discretion as in clinical practice. Sensors will be provided for replacement as needed (e.g. sensor falls off or fails internal quality checks included in the manufacture's product). Sensors may also be replaced at the subject's discretion should they observe the sensor is consistently not tracking blood glucose values as is standard practice. Subjects' CGM will be programmed with a low glucose alarm at 60 mg/dl. Subjects will also be requested to confirm episodes in which the sensor reports hypoglycemia with a capillary blood glucose meter measurement, and to treat hypoglycemia as per their home routine. At the completion of the study, CGMs devices will be collected.

Use of the FitBit Device. Combined with the initial training on CGM will be a short description of how the FitBit device works, and how the data obtained from the device will be used. Subjects will be encouraged not to make adjustments in insulin delivery based on the device readings, unless instructed by a research team member. At the completion of the study each subject will be allowed to keep FitBit monitors (valued at \$49.95 - \$99.95).

STUDY PROCEDURES:

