Insulin Pump Therapy: Participants will continue to use their own insulin pump and home blood glucose meter. All subjects will continue to receive routine care from their primary diabetes team. We propose to enact insulin dosing changes if we discover significant hyperglycemia and informing the diabetes providers of these changes." All other insulin dose changes unrelated to activity monitor data and energy expenditure estimates will be at the discretion of the primary team. We recognize that initial use of CGM may reveal previously undetected hypo- or hyperglycemia. Subjects and their families should discuss these findings with their primary diabetes team as they would for any other concerning blood glucose levels. If significant nocturnal hyperglycemia is detected, an increase in nighttime insulin basal rate will be recommended by the study team after being reviewed by the study endocrinologist. The dosing changes to address the hyperglycemia will be made by the study team directly in order to prevent delays in correction of the hyperglycemia as can occur if forced to wait for a response from the primary provider. Nevertheless, Tte recommended changes will also be sent as a powerchart message to the subject's primary diabetes care team and they will be given the option to opt out of the recommendation and contact the patient directly to address the discovered hyperglycemia. If the provider responds after the changes have been enacted then we will simply contact the family and ask them to resume their prior settings and discuss with their provider an alternative plan to treat the hyperglycemia.

Changes in Pump Therapy Based on Activity: During the first two to six weeks of the study, a baseline activity level will be established for each subject (average and standard deviation of first 14 days of available data). High activity

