days will be initially defined as any day where the activity is greater than one standard deviation above the mean. This definition, however, may need to be adjusted on a subject specific basis as it may vary due to physical fitness. Nadir glucose on increased activity days will be inputted into an adaptive basal algorithm. The algorithm is initialized with the subject's baseline insulin rate settings. Once the algorithm detects a need to modify the basal rate based on activity level, then an alternate basal profile will be recommended by the study physicians if deemed appropriate. The change will be made by the parent during one of the scheduled weekly phone calls or any other time of the week if needed. A study team member will walk the parent through the required steps to change insulin pump settings and confirm by verbal read back, screenshot or download that the pump settings are correct. Any changes to insulin pump therapy will be communicated to the subject's primary diabetes team via a note entered into the patient's BCH medical record.

Subject-Study Team communication: All subjects/families will be asked to contact the study team and perform a data download on a weekly basis. Families will be asked if they were compliant with CGM and activity monitor, if they had issues with blood glucose levels and if there were any intercurrent illnesses. Additionally, participants should contact a study team member if they experience any technical difficulties with their CGM or activity monitor, if they experience any nocturnal hypoglycemia (confirmed by home glucometer) or if they have concerns regarding a high activity day. Study team members will review daily activity data and call subject's families if an insulin dose change is recommended. A study team member will be available on page 24 hours a day.

Safety Monitoring: If CGM review reveals significant and recurrent hyperglycemia or activity-unrelated hypoglycemia, the subject's diabetes team will be alerted so that they may decide if changes to the subject's baseline insulin regimen are required. The study team may enact nighttime basal insulin dosing changes if significant nocturnal hyperglycemia is encountered while simultaneously alerting the patient's primary diabetes providers of these changes and giving them the option to change or refuse the recommendation.

d. **Definition of Primary and Secondary Outcomes/Endpoints**

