This is a pilot study to determine the feasibility of combining activity monitor data with CGM and pump data to make prospective recommendations to reduce basal insulin delivery following high activity days. There is no planned hypothesis for the pilot phase; however, planned comparisons for a larger study will be powered from the data obtained. The primary endpoint for the larger study will be a reduction in the incidence of nighttime hypoglycemia. Secondary outcomes will include the ability of activity data to predict nighttime nadir glucose.

Hypoglycemia will be defined as home meter glucose < 70 mg/dl for all subjects, CGM values below threshold for >30 minutes with no concomitant blood sugar reading (i.e. subject is sleeping at home and ignores the low glucose

alarm but the CGM is <70 for more than 30 minutes). Hypoglycemia episodes within one hour of each other will be considered as one event. Two hypoglycemic events with an intermittent blood glucose value above 70 mg/dL will be treated as a single event. Hypoglycemia and “use-of-supplemental- carbohydrate-to-prevent-hypoglycemia” will be treated identically.

5. Data Management and Statistical Analysis

One study folder, with IRB approved consent forms and case report forms (CRF), will be maintained for each subject recruited into the study. Sensor information, as provided by the manufacturer, will also be recorded on CRFs (identification numbers such as lot or serial together with expiration). Electronic data downloads for the insulin pump, containing a history of insulin delivery commands; glucose meter and glucose sensor, containing a record of all glucose values received and any alarms will be obtained weekly and the downloaded files copied to a password protected study computer in subdirectory labeled with the patient identification number. A copy of the spreadsheet used to screen blood glucose and activity data will also be placed in this directory.

a. Data Analysis Plan

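### The dosing target is the child's usual-care overnight nadir with no minimum, so for a child whose usual nadir is below 70 mg/dL the target lies inside the study's own hypoglycaemia range

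*Combined protocol and SAP*

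**What the plan says.** The specific aim (section 1) is to learn whether activity data can predict the need to "make temporary insulin pump dose adjustments to prevent nighttime hypoglycemia". Section 4.a derives the alternate basal rate from usual-care settings, with incremental changes over the three hours before the hypoglycaemic event. It then states: "Target will be the overnight nadir obtained with usual care settings". The next sentence gives a use for the error: "Residual error (CGM-target) will be used to assess the validity of using the 3 hour window prior to the event to effect lower basal". Section 4.c (Changes in Pump Therapy Based on Activity) feeds the nadir from increased-activity days into the algorithm.

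Section 4.d gives the event definition: "Hypoglycemia will be defined as home meter glucose < 70 mg/dl for all subjects, CGM values below threshold for >30 minutes". Its parenthesis makes the CGM threshold 70 mg/dL.

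The only numerical target is 110-130 mg/dL, in the preliminary simulation (section 3). It is not carried into section 4. The protocol does not say whether the usual-care nadir is a mean, a median or the lowest night, or whether it is recalculated when usual-care settings change. Section 5.a anticipates such changes.

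Several safeguards exist. A study physician approves every recommendation, CGM data are downloaded weekly, and families are asked to report nocturnal lows confirmed by meter. The primary team is alerted to "significant and recurrent hyperglycemia or activity-unrelated hypoglycemia". The "CGM will be programmed with a low glucose alarm at 60 mg/dl".

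**The concern.** A target taken from usual care is only as safe as usual care. No eligibility criterion excludes a child with low nights, and section 4.c expects some to come to light: "We recognize that initial use of CGM may reveal previously undetected hypo- or hyperglycemia". For a child whose usual nadir is 65 mg/dL, a high-activity night spent at 65 for more than 30 minutes meets the event definition and also sits exactly on target.

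The safeguards leave a gap at 60-69 mg/dL. The study-set alarm is at 60, so it gives a sleeping child no prompt for the meter check on which the family's report depends. Physician approval acts on recommendations, and a rule that reads the night as on target may issue none. The primary-team alert is for lows unrelated to activity, and section 4.a keeps activity-based advice on night rates away from that team. At stake is whether the rule stops reducing insulin too early in the children with the least room for error.

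**Working it through.** **1. The plan's own figure.** In the section 3 simulation the basal rate falls from 0.5 to 0.2 U/hr with a change threshold of 0.05 U/hr: (0.5 − 0.2)/0.05 = 6 changes, as stated.

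**2. Where that equation settles.** With a flat glucose trend, the update is (K_P/T_I) × (G − target), which is zero only at G = target. A target of 60 or 65 mg/dL therefore settles at 60 or 65. The gain is not stated. The simulation's first change needs a repeat observation at 50 mg/dL, so two errors, but not one, must reach 0.05 U/hr. Across targets 110-130 this bounds the gain at about 0.0003 to 0.0008 U/hr per mg/dL; 0.0005 is used below. The sign does not depend on it.

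For a usual nadir of 60 and an active-night nadir of 65:

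| Target | Error (mg/dL) | Update (U/hr) |
|---|---|---|
| 60 (as written) | +5 | +0.0025 |
| 70 (floor of 70) | −5 | −0.0025 |
| 80 (floor of 80) | −15 | −0.0075 |
| 110 (simulation's lower bound) | −45 | −0.0225 |

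As written, a night below 70 gives no push towards less insulin. This assumes that the trial version keeps the error term.

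**3. Size within an affected child.** The protocol gives no nadir distribution. Assume normal nadirs with a night-to-night SD of 25 mg/dL (range 15-30) and a mean active-night nadir exactly on target T. The share of active nights with a nadir below 70 is Φ((70 − T)/SD):

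| T | SD 15 | SD 25 | SD 30 |
|---|---|---|---|
| 60 | 75% | 66% | 63% |
| 65 | 63% | 58% | 57% |
| 70 | 50% | 50% | 50% |
| 80 | 25% | 34% | 37% |
| 90 | 9% | 21% | 25% |

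These shares overstate section 4.d CGM events, which need more than 30 minutes below 70.

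**4. How many children.** Assume child mean nadirs average 100 mg/dL (90-110), with between-child SD 15 (10-20), within-child SD 25 (15-30) and 14 nights.

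- *Target is the 14-night mean.* P(target < 70) = Φ((70 − μ)/√(SD_b² + SD_w²/14)). Central case: Φ(−30/√(225 + 44.6)) = Φ(−1.83) = 0.034, or 0.7 of 20. Highest (90, 20, 30): Φ(−20/21.5) = 0.177, or 3.5 of 20. Lowest (110, 10, 15): Φ(−40/10.8) = 0.0001, or about 0.
- *Target is the lowest of 14 nights.* P is the average over child means m of 1 − (1 − Φ((70 − m)/SD_w))^14. Central case: 0.73, or about 15 of 20. Over the same ranges it runs from 2.7 (110, 10, 15) to 19.1 (90, 10, 30), so about 3 to 19 of 20.

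**The case against.** The strongest reply is that the update rule used in the trial is not stated. Section 3 promises only a version of the simulated algorithm. Section 4.a assigns the residual to checking the three-hour window and places the changes in the hours before a hypoglycaemic event. On that reading, an active night at 65 could itself prompt a reduction. This stands. A reader might infer that the rule scores such a night as a success, or would raise insulin after it; the documents establish neither. The positive update in the example comes from the simulation equation, whereas the activity component is meant to lower basal rates.

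Second, a usual nadir below 70 suggests recurrent lows unrelated to activity, which sections 4.a and 4.c leave to the primary team. The usual-care nadir fits that division of work and is a sensible comparator for isolating the activity effect. This stands in part: the team may correct the baseline, but correction is discretionary and no recalculation of the target is specified.

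Third, a reader might take the lowest-night figures to mean that most of the cohort is affected. The protocol never says the lowest night is used. The only nadir summary it gives, in section 5.a, is a weekly mean, though for analysis rather than for the target.

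Fourth, low active nights are not hidden from the study. Section 5.a analyses hypoglycaemia by chi-square, logistic regression and GEE, and plots weekly time below target. They are absent only from the feasibility criterion, which asks whether data can be assembled and recommendations are accepted.

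**Conclusion.** The concern holds as a conditional statement about the target. Sections 4.a and 4.d together allow a dosing target inside the study's own hypoglycaemia range, and no eligibility criterion, alarm or review step imposes a floor. That an active night below 70 could then draw no call to reduce insulin depends further on the trial keeping the section 3 error term.

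The number of children is unknown. On the assumed inputs it is probably small, about 0 to 3.5 of 20 with a mean nadir. The wider span with a lowest-night target mainly shows why the summary must be stated. Within an affected child, a target of 60-65 would leave more than half of active-night nadirs below 70 (57% to 75% across the SDs tried). The point should be corrected because the rule guides insulin dosing in children and the remedy is cheap. Confidence is medium, given the unstated update rule and the assumed distributions.

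**What to change.** - Keep the usual-care nadir as the comparator for the activity effect. Define it as the mean of nightly nadirs on ordinary (not high-activity) nights, recalculated whenever usual-care settings change.
- Set the dosing target to the higher of that value and one prespecified floor above 70 mg/dL, chosen by the study physicians, for example 80. A floor of exactly 70 gains little: for a target of 65 it moves the share of nadirs below 70 from 58% to 50%, against 34% at 80 (SD 25).
- State that a night meeting the section 4.d definition is never treated as on target.
- In section 5.a, report the number of hypoglycaemic high-activity nights that produced no recommendation.

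The cost is a text change and one count from data already collected, with no added procedures. The downside is that in children with a low usual nadir the rule will partly correct the baseline setting as well as the activity effect. Report those children separately and watch for overnight highs.

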In the equation, the basal rate from midnight to 3 am on a future day, is denoted with a superscript $N+1$, is calculated from the value used on the current day, denoted by superscript N . Recommendations to increase or decrease the basal rate are based not just on whether the CGM glucose value is below target, but also on what the rate of change of glucose is at that time. Thus, a 3 AM CGM value that is consistently at target but decreasing may result in a recommendation to decrease the midnight to 3 AM basal rate, and a value is above target but approaching target at a desired rate may leave the basal rate un-changed, the desired rate being set by parameter T_I . Changes are not made from day-to-day; rather, the value is updated each day but needs to pass a threshold set by the user (0.05 U/hr in this simulation). Thus, a value slightly above target range on one day, and slightly below target on a subsequent day,

has no net effect, with a change only occurring following an interval where the values are consistently above or below target. In the simulation study, the pump basal rates were initially set to be higher than needed, leading to a 3 AM glucose value of 50 mg/dL on the first observation (simulating a night following a high level of activity during the day). For the values of K_P and T_I chosen, the first recommended change requires a repeat occurrence at 50 mg/dL, and a total 6

[figure not shown]

Figure 1. Simulated pump adaptation showing changes in 3 am glucose over 28 days of adaptive pump therapy.

changes are required to decrease the basal rate from the initial 0.5 U/hr to 0.2 U/hr. Different values of K_P and T_I lead to more rapid or slower adaptation. As well, the target range can be decreased, but will require additional pump adjustments that the physician or patients may find unnecessary.

Figure 2.

$$BASAL_{0-3}^{N+1} = BASAL_{0-3}^N + K_P(G_{3am} - \text{target})/T_I + K_P \frac{dG_{3am}}{dt}$$

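### The 3-hour window is judged by raw residual error with no comparator, so regression to the mean can make it look more effective than it is

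*Combined protocol and SAP*

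**What the plan says.** Section 4.a (Study design) starts the alternate rate from the child's usual settings, "from which to make incremental changes in the 3 hour interval leading up to the hypoglycemic event". It then fixes the reference: "Target will be the overnight nadir obtained with usual care settings". The next sentence gives the test: "Residual error (CGM-target) will be used to assess the validity of using the 3 hour window prior to the event to effect lower basal". It does not say which nights enter the residual, which CGM value is used, what residual counts as valid, or what it is compared with. There is no control arm.

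Nights become eligible by activity: "an alternate basal insulin rate will be recommended on days considered to be increased activity days". Under Changes in Pump Therapy Based on Activity (section 4.c), high activity "days will be initially defined as any day where the activity is greater than one standard deviation above the mean". The same text says "Nadir glucose on increased activity days will be inputted into an adaptive basal algorithm", and an alternate profile follows only once the algorithm detects a need.

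Section 3 describes the algorithm in simulation. Error accumulates against a threshold (0.05 U/hr there), and "the first recommended change requires a repeat occurrence at 50 mg/dL". The trial's own gain, time constant and threshold are not given.

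The Data Analysis Plan (section 5.a) does not mention the residual.

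**The concern.** Eligibility depends on activity, but the start of the alternate rate depends on glucose: it begins after a run of low nadirs. Such a run is partly the child's true response to activity and partly chance. The chance part does not persist, so later nadirs rise on average even if the new rate does nothing. Because the target is the child's usual nadir, this recovery moves the residual toward zero, which is the direction that reads as success.

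Without a comparator, a small residual after the change can mean that lowering basal in those three hours worked, or that the nights before the change were unusually low. What is at stake is the stated judgement about the window: whether it is the right place to act, and how well it appears to act.

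**Working it through.** The plan gives no figure for this assessment, so there is nothing to reproduce. The check sets the insulin effect to zero and asks how far the residual moves.

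**Inputs from the protocol.** Hypoglycemia cut-off 70 mg/dL (section 4.d); high-activity day above mean + 1 SD (section 4.c); target equal to the usual-care nadir (section 4.a), read here as the child's mean.

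**Assumptions, not in the protocol.** Mean usual nadir μ of 90 to 110 mg/dL; night-to-night SD 20 or 30 mg/dL; activity shifts the nadir by d = 0, −10 or −20 mg/dL; correlation ρ between nights of 0 or 0.3; a change is triggered when summed residuals reach −60 or −120 mg/dL.

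**Step 1: one low night, then the next (an upper bound).** With a = (70 − μ − d)/SD, the mean residual on a night selected for a nadir below 70 is d − SD·φ(a)/Φ(a). The next residual is d + ρ × (selected residual − d).

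- μ = 100, SD = 30, d = 0: a = −1, and the selected residual is −30 × 0.2420/0.1587 = −45.8. The next is 0 at ρ = 0 and 0.3 × (−45.8) = −13.7 at ρ = 0.3.
- μ = 100, SD = 30, d = −20: a = −0.333, and the selected residual is −20 − 30.6 = −50.6. The next is −20 at ρ = 0 and −20 − 0.3 × 30.6 = −29.2 at ρ = 0.3.

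Over the full range of assumptions, the share of the gap that closes by chance is 70% to 100% at d = 0 and 31% to 65% at d = −20.

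**Step 2: an accumulating trigger, closer to section 3.** This simulates 100,000 series of independent high-activity nights, with up to 13 nights in which to trigger. It compares the mean residual up to the trigger with the mean over the next three high-activity nights (mg/dL).

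| d | SD | Trigger sum | Up to trigger | Next three | Apparent gain |
|---|---|---|---|---|---|
| 0 | 20 | −60 | −13.0 | 0.0 | 13.0 |
| 0 | 20 | −120 | −14.7 | 0.3 | 15.0 |
| 0 | 30 | −60 | −20.4 | 0.1 | 20.5 |
| 0 | 30 | −120 | −20.0 | 0.1 | 20.1 |
| −10 | 20 | −60 | −16.3 | −10.0 | 6.3 |
| −10 | 20 | −120 | −16.6 | −10.0 | 6.6 |
| −10 | 30 | −60 | −23.1 | −10.0 | 13.1 |
| −10 | 30 | −120 | −21.8 | −10.0 | 11.8 |
| −20 | 20 | −60 | −24.6 | −20.0 | 4.6 |
| −20 | 20 | −120 | −23.0 | −20.0 | 3.0 |
| −20 | 30 | −60 | −29.9 | −20.0 | 9.9 |
| −20 | 30 | −120 | −27.2 | −20.1 | 7.1 |

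After the trigger the residual settles at d. It reaches target only when activity has no effect on the nadir.

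**Step 3: no selection on glucose.** If the residual is averaged over all high-activity nights, its expectation under an inert change is d both before and after. The apparent gain is zero.

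**Step 4: which comparator works.** In a no-effect simulation (assumed mean 105, SD 30 mg/dL, 20 children), a simple within-child before/after contrast still showed a false gain of about 1 to 10 mg/dL, because the nights before a trigger are themselves selected for lows. A mixed model over all nights was biased by about 0 to 1 mg/dL, with a standard error of about 4 to 6. The leftover bias varies with the settings, so this shows a large reduction, not exact removal.

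**The case against.** The strongest reply is that a reader might infer that the plan tests the window on nights picked for hypoglycemia, and so is bound to validate it. The documents do not say that.

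- **Selection.** Nights are chosen by activity, and nadirs from high-activity days in general feed the algorithm. The hypoglycemic event places the window; nothing restricts the residual to nights after an event. This stands. What remains is that the change itself waits for low values.
- **Damping.** Section 3 requires consistent deviations, which guards against one-off lows. This also stands, although that text describes the simulation. Step 2 shows that damping reduces the effect without removing it.
- **Reference.** The residual is measured from the target, not from the event night. If activity truly lowers the nadir, as the protocol's background suggests, an inert change leaves the residual below target, which would count against the window. This stands too, but no acceptance limit says how large a shortfall would count, and whether activity lowers the nadir is what the study sets out to learn.
- **Size.** A reader might compute a false rise of about 57 mg/dL: with an assumed mean of 110 and SD of 35, the mean nadir on nights below 70 is 52.6, and 110 − 52.6 = 57.4. That needs selection on a single night, zero correlation and no activity effect. It is not a fair estimate for this design.
- **Consequence.** A reader might also infer that the inflated residual would set the larger study's effect size. Section 4.d says that study will be powered from these data, but its primary endpoint is the incidence of nighttime hypoglycemia, and nothing ties the residual to it.

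**Conclusion.** The concern holds in a limited form. The raw residual has no comparator and cannot tell an insulin effect from chance recovery, so it can make the window look more effective than it is. It will not necessarily make an inert window look valid. That needs activity to have no effect on the nadir and little correlation between nights.

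Under an accumulating trigger with an inert change, the false gain is about 13 to 20 mg/dL at d = 0, about 6 to 13 at d = −10 and about 3 to 10 at d = −20. In the last two cases the residual stays below target. These figures rest on assumed SDs, trigger sums and independent nights; the protocol supplies none of them.

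The pilot is unpowered and has no planned hypothesis. Its feasibility criterion (data assembled, recommendations accepted in a majority of cases) does not use the residual, so that conclusion is not at risk.

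**What to change.** Add the assessment to section 5.a and state that the raw residual will not be interpreted alone. Fit one mixed model of nightly residual (or nadir) over all nights of all children, with a child random effect, an indicator for a high-activity day and an indicator for the alternate rate being in force. The last coefficient, with its interval, is the evidence on the window. Say which CGM value enters.

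The reference must be every high-activity night on usual settings, from all children, including those who never change rate. It should not be limited to nights after an event, or to the nights before the change in children who later changed, because those are selected for lows.

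This changes analysis wording only and needs no new data. The price is a wider interval. If activity is roughly normal, about 15.9% of days exceed mean + 1 SD, so a 14-day baseline gives about 14 × 0.159 = 2.2 such nights per child, and six weeks about 42 × 0.159 = 6.7. The standard error of about 4 to 6 mg/dL in step 4 is similar in size to the smaller false gains, so the pilot estimate will be imprecise and should be reported as such.
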